**Figure 3. Full factorial experimental design (3: 2x2x2)**

Group	Experimental conditions			Effects of interest				Notes
	Factor A	Factor B	Factor C	A	B	C	A*B	
1	Standard FN	Standard FN	Standard FN	-1	-1	-1	+1	Least innovative model (standard FN)
2	Standard FN	Standard FN	Enhanced monitoring	-1	-1	+1	+1	
3	Standard FN	Community visits	Standard FN	-1	+1	-1	-1	
4	Standard FN	Community visits	Enhanced monitoring	-1	+1	+1	-1	
5	Enhanced technology	Standard FN	Standard FN	+1	-1	-1	-1	
6	Enhanced technology	Standard FN	Enhanced monitoring	+1	-1	+1	-1	
7	Enhanced technology	Community visits	Standard FN	+1	+1	-1	+1	
8	Enhanced technology	Community visits	Enhanced monitoring	+1	+1	+1	+1	Most innovative model

"Standard FN" = primary care based FN; "Enhanced technology" = additional use web portal ACT-MD; "Community visits" = visits at home or in the community; "Enhanced monitoring" = additional screening conducted by FPs between pediatric visits.

**Randomization Process.** Before initiation of FN and after obtaining parent consent, FPs will randomly assign each family an experimental condition using a computer program. The computer program will use both a randomly-generated number and "minimization procedures" to minimize imbalances across conditions with respect to target variables, including family/child characteristics (e.g., education,

gender, race/ethnicity, screening score). In this procedure, the first participant is assigned at random. Subsequent participants have a  $p$  chance of being randomly assigned and a  $1-p$  chance of being automatically assigned to the condition that would most reduce imbalance based on selected sample characteristics. Minimization procedures are considered best practices for sequential assignment. Families with more than one child enrolled will participate in the same random condition for all children.

**Number of study groups/ arms and descriptions.** Randomization across 4 binary factors results in 16 possible combinations of the 4FN delivery strategies (see **Figure 3**). In total, we plan to enroll 304 families:  $n=19$  for each of the 8 cells. 304 families represent around 715 unique human subjects with 304 parent/legal guardian, 304 index children, 107 additional siblings for families with more than one child enrolled.

**Planned variation in intervention strategy.** As seen in figure 3 above, study participants will be assigned to varying combinations of intervention delivery strategies or factorials:

**Strategy A** - Care Coordination (Usual care v. Enhanced: Technology assisted);

**Strategy B** - Mode of Delivery (Clinic-based v. Clinic + Community); and

**Strategy C** - Symptom Tracking (Pediatric Surveillance at annual well-child visit v. Enhanced: Tracking at 3, 6, 9, and 12 months).

**Strategy D:** Visit structure (individually tailored vs standardized, schedule-based visits with families)

**Methods for collecting data for assessment of study objectives.** As seen in **Table 1**, data regarding use of services will be collected and obtained for analysis using the EHR. This EHR data will include FP's template documentation of FN activities, and service use measures (engagement in services measures). Clinical Measures will be sent to families via Epic's mobile app MyChart program, REDCap, administered via telephone or HIPAA compliant Zoom by the study RA or sent to the parent by mail with a return stamped envelope. Once the measures are received by mail, the responses will be manually entered into our RedCap database and the paper copies stored in a locked filing cabinet in a locked office. In cases where families are unable to use MyChart due to limited access to a computer or limited computer literacy and the FP will contact them and enter responses to measures into the appropriate EHR form or mail the parent a copy.

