family, they would like services and would like to work with the FP, the family will have the opportunity to enroll in the study and be randomized to a study condition. This group of parents will be called the “watchful waiting” group. The watchful waiting group will NOT be consented at the time of initial contact. If they are interested in pursuing services for their child at the time of recontact, the parent and child will be offered study participation at that time and will have the opportunity to consent to or decline participation. We have included this group based on our clinical experience. We find that many families wish to delay services for a number of reasons including life events (family moving, expecting a new baby) and timing (child going away for the summer, want services through school and school ending or not in session). We would like to make study participation available for such families.

The FP will administer the baseline assessment measures and then the family will be randomized (on an individual basis through a randomization generator centralized with the study statistician) to a study condition. If the family declines participation, the FP will refer the family to health center care managers and have no further contact with the family.

**Randomization Procedures.** Before initiation of FN, FPs will assign each family an experimental condition using a computer program. The computer program will use both a randomly-generated number and “minimization procedures” to minimize imbalances across conditions with respect to target variables, including family/child characteristics (e.g., education, gender, race/ethnicity, screening score). In this procedure, the first participant is assigned at random. Subsequent participants have a p chance of being randomly assigned and a 1-p chance of being automatically assigned to the condition that would most reduce imbalance based on selected sample characteristics. Minimization procedures are considered best practices for sequential assignment. Families with more than one child enrolled will participate in the same random condition for all children.

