### **12.2 Sample Size Determination**

#### **Sample Size and Power.**

Of the three measures to operationalize engagement, we powered our study on the dichotomous variable “receipt of BH services within 90 days” - the most conservative estimate. We base our power calculation on the number needed to detect the smallest differences in primary outcomes that are of clinical importance. Our formative work with staff at DotHouse and other community health centers indicates that a relative risk of approximately 25% would be considered clinically significant. Therefore, if 60% of families in the core navigation condition engage in mental health services (estimates based on our prior work), to detect a 25% difference (i.e. 75% of families in any of the FN delivery conditions engage in services), and assuming 2-tailed tests and a type 1 error rate of 5%, approximately 304 participants are required to detect this effect (n=38 in each of 8 cells). Although 304 participants are required for our power analysis, we will be enrolling 715 human subjects which include 304 parent/legal guardian, 304 index children for primary analysis and around 107 siblings for families with more than one eligible child. Additional sibling analysis will be done to explore differences in service goals etc.

We expect strong effects of study mediators, in particular fidelity variables and variables that are central to our theoretical model, such as increased parent capacity. Following published guidance based on an empirical review, we estimate that our design will have at least 80% power to detect mediation effects where the paths from independent variable to mediator and from mediator to outcome are of at least small-to-medium effect (ES=.26). Given that our mediation analyses are designed to support decisions regarding intermediate outcomes to be tracked for quality control and assurance, effect sizes less than this magnitude are not considered to be clinically important. In contrast, analyses of patient-level treatment moderators are exploratory as we have no evidence to support hypotheses of any effect.

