**Objective 1: Effectiveness of FN delivery strategies.**

Following an intent-to-treat model, multiple regression models will be used to test hypotheses regarding the main effects of the three delivery strategies and their combined effects on the study's primary outcome, engagement in appropriate mental health services. A series of increasingly complex models will be constructed to address each specific index of outcome. For example, a logistic regression analysis will test receipt of behavioral health services within 90 days. Cox regression (proportional hazards) analyses will then be used to test the effect of each factor on time-to-scheduling date, and then on time-to-receipt of behavioral health services (with *time to third-next-available appointment* included as a covariate). Given that children may be referred to behavioral health services beyond those designated as primary in their initial visit, multi-level models will then be constructed with time-to-receipt of each behavioral health service as an outcome and with services clustered within child. Similarly, engagement in services will first be analyzed with logistic regression using our definition of engagement in care as a binary outcome, with subsequent multilevel models to analyze engagement in multiple services.

For outcomes involving engagement with services, sensitivity analyses will be conducted in which missing data from the EHR is interpreted as failure to engage in services. While we do not hypothesize interactions among the delivery strategies, these will also be explored. Following recommendations for factorial designs, effect coding (not dummy coding) will be used for experimental conditions to assess for interaction. In addition to evaluating effects "at the margins" using all available cells, results for each individual cell will also be reported, as will simple main effects.

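### Families are allocated by minimisation on baseline characteristics, but section 12.3 names none of them as covariates in the Objective 1 models, so the reported standard errors will be too large if those characteristics predict the outcome

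*Combined protocol and SAP*

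**What the plan says.** **Allocation.** The randomisation paragraphs of sections 5 and 9 describe a computer program used to "minimize imbalances across conditions with respect to target variables, including family/child characteristics". Apart from a random element p, it places each family in the condition that most reduces imbalance on selected variables, "including family/child characteristics (e.g., education, gender, race/ethnicity, screening score"). The list is given by way of example, and p has no value.

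**Analysis.** Section 12.3, Objective 1, models the effect-coded delivery strategies. For the primary outcome, "a logistic regression analysis will test receipt of behavioral health services within 90 days"; Cox and multilevel models follow. The only covariate named in any of these models is the third-next-available appointment time, in the Cox analysis, and it is not among the listed allocation variables.

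**Other uses of baseline data.** The overview of 12.3 compares baseline characteristics across conditions to check balance. Race/ethnicity and symptom severity reappear under Objective 2 as moderators, in stratified analyses. Nothing in the document puts the allocation variables in the primary model or gives a reason for leaving them out.

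**The concern.** Minimisation removes most of the chance imbalance on the chosen variables. If those variables predict the outcome, the estimated factor effects vary less from trial to trial than they would under simple randomisation. An unadjusted logistic model does not know this: it computes its standard error as if the imbalance could still have occurred. The test then rejects less often than its nominal 5%, and the confidence intervals are too wide.

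The protocol gives a qualitative reason to expect some prognostic value. Section 3.1 describes later diagnosis and delayed treatment for low-income and minority children, and the team chose these variables for balancing.

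At stake is how the main effects are reported in a trial whose purpose is to choose which delivery components go forward. An over-wide interval makes it a little easier to discard a useful component. Section 12.2 also leaves little slack, because its sample size gives almost exactly 80% power for an unadjusted test. Finally, 12.3 plans balance tests but does not say what follows from a significant one, so the choice of covariates stays open until the data are seen.

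**Working it through.** **1. The plan's own figure.** Inputs from section 12.2: "assuming 2-tailed tests and a type 1 error rate of 5" per cent; "if 60% of families in the core navigation condition engage in mental health services"; "75% of families in any of the FN delivery conditions engage in services". Power for this outcome is not stated (the 80% in that section concerns mediation), so 80% is assumed. For a pooled two-proportion test with mean rate 0.675:

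n per factor level = [1.960 × √(2 × 0.675 × 0.325) + 0.842 × √(0.60 × 0.40 + 0.75 × 0.25)]² / 0.15² = (1.298 + 0.550)² / 0.0225 = 151.9, so 152.

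The total is 2 × 152 = 304, which matches the plan, with power of 80.0%. The calculation uses no covariates. It depends only on 152 families per factor level, not on how many cells they are spread over.

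**2. Simulation under the plan's allocation.** 304 families, 16 conditions, minimisation on four baseline factors, main-effects logistic models with and without those factors, two-sided 5% Wald tests, marginal rates of 60% and 75%. Assumed, because the documents do not give them: p = 0.2 and the prognostic strength. There were 1,500 replicates per setting. Monte Carlo error is at most √(0.05 × 0.95 / 1,500) = 0.6 points for type I error and √(0.8 × 0.2 / 1,500) = 1.0 point for power.

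| Latent variance explained (assumed) | Type I error, unadjusted | Type I error, adjusted | Power, unadjusted | Power, adjusted | Difference in power (points) |
|---|---|---|---|---|---|
| 0% | 4.9% | 5.3% | 80.9% | 81.1% | 0.2 |
| 5% | 4.9% | 5.7% | 80.9% | 82.1% | 1.2 |
| 10% | 4.2% | 5.3% | 80.8% | 83.1% | 2.3 |
| 20% | 3.4% | 4.9% | 82.4% | 86.7% | 4.3 |

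At 5% of variance the unadjusted test cannot be told apart from 5%. The conservatism becomes visible from about 10%.

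**3. A second, larger run.** 5,000 replicates, same p, with strength measured as the share of variance of the binary outcome (a different scale from the table):

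- 0%: type I error 5.1% unadjusted and 5.4% adjusted; power 80.4% and 80.8%.
- About 2%: 5.0% and 5.5%; power 81.7% and 82.8%.
- About 9%: 4.3% and 5.5%; power 80.8% and 83.7%.
- About 25%: 2.7% and 5.3%; power 83.1% and 89.8%.

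Monte Carlo error is about 0.2 points for type I error and 0.6 for power. With simple randomisation in place of minimisation (1,500 replicates), unadjusted type I error was 5.2% at about 9% and 5.4% at about 25%. The conservatism therefore comes from minimising and then not adjusting. With no random element (p = 0) it was 4.5% at about 9%, so the result there does not hinge on p = 0.2.

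**4. How much too large is the standard error?** If the true type I error is α*, the implied ratio of reported to true standard error is z(1 − α*/2) / 1.960. At 10% of latent variance this is 2.034 / 1.960 = 1.04; at 20% it is 2.120 / 1.960 = 1.08. Reported standard errors are about 4% and 8% too large.

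**5. Is information lost?** Put both tests at a true 5% level: size-corrected power = Φ[z(1 − α*/2) + z(power) − 1.960].

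- 10%: unadjusted Φ(2.034 + 0.871 − 1.960) = 82.7%; adjusted Φ(1.935 + 0.958 − 1.960) = 82.5%.
- 20%: unadjusted Φ(2.120 + 0.931 − 1.960) = 86.2%; adjusted Φ(1.969 + 1.112 − 1.960) = 86.9%. Direct size correction in the simulation gives 86.4% and 86.7%.

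The gap nearly disappears. Most of the power difference in the table is a difference in test size.

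**The case against.** **Silence is not exclusion.** Section 12.3 speaks of a series of models of growing complexity and neither lists nor forbids baseline covariates. This stands: a reader might infer that the plan has decided against adjustment, and the text does not support that. The gap is in pre-specification.

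**No prognostic information is thrown away.** A reader might infer that the unadjusted analysis wastes what the covariates know. It does not, to any material degree: minimisation has already put that information into the allocation, and step 5 shows near-equal power at equal size. What remains is a standard error and interval that are too wide.

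**The variables may not be prognostic.** The documents give no figure. If they are not, nothing is gained. This stands, and it limits the size of the point but not its direction.

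**The remedy has its own cost.** The adjusted Wald test ran at 4.9% to 5.7% in the table and at 5.3% to 5.5% in the larger run, including 5.4% with covariates of no value. Part of the apparent gain in power reflects this. It stands, and argues for few parameters: at an average rate of 67.5% there are only about 304 × 0.325 = 99 families without the outcome.

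**The list is open-ended.** With variables given only as examples and p unspecified, adjusting for all of them is not yet a defined instruction. This also stands, and the fix has to start there.

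**Conclusion.** The point holds as one of calibration and pre-specification. Followed as written, the plan allocates by minimisation and analyses as if it had not. Where the balancing variables explain 10% to 20% of latent outcome variance, the unadjusted test runs at about 4.2% to 3.4% in place of 5%, standard errors are about 4% to 8% too large, and the test as run gives up roughly 2 to 4 points of power. At 5% of variance the power cost is about 1 point; at zero there is essentially none.

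These sizes rest on an assumed p of 0.2, assumed prognostic strengths, and the four example variables standing in for the full list. The direction is secure whenever the variables are prognostic.

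Two further inferences are not supported. Type I error is not inflated by the plan as it stands, since the deviation is on the conservative side. The sample size is not undermined either: 304 families reproduce exactly from the plan's inputs, and the unadjusted test reaches about 80% power or slightly more in every setting examined.

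**What to change.** 1. In the randomisation paragraphs of sections 5 and 9, replace the examples with the final list of minimisation variables and their categories, and give p.
2. In 12.3, Objective 1, state that the primary logistic model, and the Cox and multilevel models, contain the effect-coded factors plus those variables. If the baseline screening score is among them, add an indicator for the instrument, because the younger and older children are screened with different tools.
3. Keep the number of parameters per covariate small, to limit the slight excess over 5% in the adjusted Wald test.
4. Report standardised marginal rates and risk differences, because an adjusted odds ratio is conditional on the covariates and is not the marginal 60% versus 75% contrast on which the trial was sized.
5. Keep the unadjusted model as a sensitivity analysis.

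The cost is a few sentences, settled before outcome data are analysed. No extra families are needed, and no new data, since the allocation program must already hold these values.
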